TIPN manifests via several different pathophysiological mechanisms that can be assessed by current modalities; none of which have yet emerged as a widely-adopted standardized approach. Taxane disruption of microtubules impairs the normal self-maintenance of neurons which is evident structurally as the degeneration of distal axons and nerve terminals. Inflammatory changes occur as the innate immune system responds to these damaged and leaking organelles. Genetic polymorphisms in neuronal and inflammatory cells contribute to individual variability in TIPN vulnerability. Functionally, as a neuronal myelin sheath deteriorates it increases the membrane surface area through which current must flow, slowing electrical conduction velocity and weakening its signal amplitude. Finally, as a result of the above mechanisms, degradation and inflammation can alter large peripheral nerves to the point that gross anatomic changes are evident on imaging.

Ultrasound (US) is a non-invasive, non-irradiating, emerging imaging modality which can be used to assess peripheral nerves. Nerve fiber cross-sectional area (CSA), echogenicity, and vascularity are assessed and provide an indication of nerve health and potential pathology. The majority of US data have been published on detection of entrapment syndromes such as carpal tunnel syndrome. In these cases the most common US findings include nerve enlargement, decreased echogenicity proximal to the entrapment, and an increase in nerve vascularity.⁷ Other studies have found that US can detect other peripheral nerve lesions or neuropathies, with the most reliable finding a change in nerve CSA. Ultrasound measurements of the sensory sural nerve at the distal calf in healthy participants without neuropathy had an average CSA of 5.3 mm² with standard deviation 1.8 mm² for a normal reference range of 1.7-8.9 mm².⁸ Another ultrasound study assessed the sural nerve more distally at the ankle and found a smaller CSA which was significantly enlarged ($p < 0.001$) in patients with diabetic

A Pilot Study Using Ultrasound for the Detection of Taxane-Induced Peripheral Neuropathy
Wake Forest Baptist Comprehensive Cancer Center (WFBCCC)
CCCWFU # 97217

polyneuropathy as compared to healthy controls (mean/standard deviation 2.59 / 0.96 mm² as compared to 1.40 / 0.59 mm²).⁹

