4.6 Diagnostic testing (Encounter 3)

Participants will be referred to Diagnostic Neurology clinic for and abbreviate neurological exam to assess strength of the tibialis anterior and gastrocnemius and deep tendon reflex exam of the Achilles tendon on the limb to be examined in nerve conduction studies and ultrasound evaluation during this encounter. Further, a skin biopsy will be obtained. These tests will be completed at a single visit and no further follow-up with neurology is required as part of the study protocol. All of these studies are considered standard clinical tests for the evaluation of peripheral neuropathy and sensory neuropathy. Patients will receive a Visa gift card upon completion of the neuropathy assessment.

Peripheral nerve US technique and reference values for the sural sensory (measured at the ankle) and tibial motor nerves are based on institutional data and standard institutional practice. These reference values were de-identified historical data which have also been published by Cartwright et al.(2008) ⁸ as noted in the Introduction and Background section. Peripheral nerves will be assessed at non-compressive sites with a routine 15Hz linear probe. If available, a higher resolution 70Hz linear probe may be used – this would allow for descriptive characterization of nerve changes and would not

A Pilot Study Using Ultrasound for the Detection of Taxane-Induced Peripheral Neuropathy
Wake Forest Baptist Comprehensive Cancer Center (WFBCCC)
CCCWFU # 97217

be anticipated to cause variability in terms of CSA measurement as compared to the standard 15Hz US.

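### Sections 1.0 and 4.6 give two different sites (distal calf, ankle) for the same healthy sural reference data, so the landmark behind the sural control comparison (objective 2.2.1) must be confirmed

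*Combined protocol and SAP*

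**What the plan says.** Section 1.0 gives the healthy sural reference, citing reference 8: "Ultrasound measurements of the sensory sural nerve at the distal calf in healthy participants without neuropathy had an average CSA of 5.3" mm², with SD 1.8 mm². It then describes a second study that "assessed the sural nerve more distally at the ankle and found a smaller CSA". At that ankle site, patients with diabetic polyneuropathy had "mean/standard deviation 2.59 / 0.96" mm² "as compared to 1.40 / 0.59" mm² in healthy controls.

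Section 4.6 covers "Peripheral nerve US technique and reference values for the sural sensory (measured at the ankle) and tibial motor nerves" and says that these "are based on institutional data and standard institutional practice". It continues: "These reference values were de-identified historical data which have also been published", cites reference 8 and points back to the Introduction. On where to place the probe it adds only "Peripheral nerves will be assessed at non-compressive sites".

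Section 6.1.2 powers the sural comparison on 5.3 and 1.8 mm² without naming a site, and claims more than 80% power for a difference of 1.3 mm². Sections 6.2 and 6.3 test it with a two-sample t-test against the individual control data.

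**The concern.** One data set carries two anatomical sites. Section 4.6 sends the reader to the Introduction for the values, and the Introduction gives a different site. The two labels cannot be read as synonyms, because Section 1.0 itself contrasts them and attaches a smaller CSA to the ankle.

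Objective 2.2.1 compares patients with historical controls, so nothing in the design balances the scanning site between the groups. If the sites differ, the anatomical difference goes straight into the estimated group difference. The expected effect of neuropathy is enlargement, while a more distal scan in patients would make their nerves look smaller. The test would then tend to miss a real enlargement and could report a shrinkage that is not there.

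**Working it through.** **Step 1. Can the rest of the protocol settle the site?**

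| Place | What it gives on the sural ultrasound site |
|---|---|
| 1.0 | Distal calf for the reference-8 controls; ankle for a different study |
| 4.2, calendar note d | Names the nerves only |
| 4.6, ultrasound text | Ankle for technique and reference values together; non-compressive sites |
| 4.6, nerve conduction text | An exact landmark at the lateral malleolus, but for electrodes, not the probe |
| 6.1.2, 6.2, 6.3 | No site |
| Appendix H | A blank field for probe location |

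Nothing resolves the conflict. Appendix H can record where a patient was scanned. It cannot show where the controls were scanned, and it does not hold all patients to one level.

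**Step 2. Reproduce the plan's figure.** Inputs from 6.1.1 and 6.1.2: 22 patients, 60 controls, SD 1.8 mm² in both groups, difference 1.3 mm², two-sided 0.05.

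- SE = 1.8 × √(1/22 + 1/60) = 0.449 mm²; df = 22 + 60 − 2 = 80; critical t = 1.990.
- Noncentrality = 1.3 / 0.449 = 2.90, so power = 81.7%. The stated figure of more than 80% is confirmed, provided both groups share one site.

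**Step 3. Add an assumed site offset.** Let *o* be the amount by which healthy CSA at the patients' site falls below that at the controls' site. The documents give no such figure, so it is an assumption shown as a range.

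- False 'smaller' = P(t < −1.990) with noncentrality −*o* / 0.449.
- Power for a true +1.3 mm² = P(t > 1.990) with noncentrality (1.3 − *o*) / 0.449.

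| Offset (mm²) | False 'smaller' | Power for +1.3 mm² |
|---|---|---|
| 0 | 2.5% | 81.7% |
| 0.25 | 7.9% | 63.8% |
| 0.5 | 19.5% | 42.1% |
| 1.0 | 59.6% | 9.7% |

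**Step 4. Sensitivity to the SD and the form of the test.** If patients are scanned at the ankle, their SD may be nearer the ankle values in Section 1.0 (0.59 to 0.96) than 1.8. The plan does not say whether the t-test is pooled or Welch. The figures below come from 400,000 simulated trials per setting, with control SD 1.8; each range spans the two patient SDs.

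| Offset (mm²) | Pooled: false 'smaller' | Pooled: power | Welch: false 'smaller' | Welch: power |
|---|---|---|---|---|
| 0 | 0.2–0.6% | 94–97% | 2.5% | 98.5–99.8% |
| 0.25 | 2.6–4.1% | 78–84% | 12–15% | 92–98% |
| 0.5 | 15–17% | 50–53% | 36–46% | 72–85% |
| 1.0 | 73–79% | 4–6% | 89–96% | 16–20% |

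Measured against its own zero-offset row, every setting moves the same way: more false 'smaller' results and less power for enlargement.

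**What is not used.** The two healthy means in Section 1.0 differ by 5.3 − 1.40 = 3.9 mm². They come from different studies, so population, equipment and technique are mixed with site. That gap is not an estimate of the offset.

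**The case against.** The best defence is that one label is simply wrong. Section 4.6 puts technique and reference values in one sentence, under one parenthesis, and bases both on the institution's own data and practice. That points to a single shared site. No section says that patients are scanned at one site and controls at another. On this reading the comparison is sound and one word needs correcting. This is at least as plausible as a real mismatch, and it stands as a limit on the concern. It does not remove the concern: the reader cannot tell which label is wrong, and an operator who follows Section 4.6 could scan at a level the controls were not scanned at.

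Three further points stand in part. The direction of the bias rests on a contrast between two studies, and the offset is unknown. At 0.25 mm² the pooled test with the smaller patient SDs is hardly harmed: false 'smaller' results stay near the nominal 2.5% and power near the planned 80%. At 0.5 mm² and above, the false-result rate is well over nominal in every setting. Finally, Appendix H allows a mismatch on the patient side to be traced afterwards, but not on the control side.

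**Conclusion.** The contradiction is certain and lies in the protocol's own text. The bias is conditional. If both groups share one landmark the offset is 0, the 81.7% power stands and only wording needs correcting. If patients are scanned more distally than the controls were, the sural test leans towards a false 'smaller' finding and away from detecting enlargement. At an assumed offset of 0.5 mm², the false 'smaller' rate is 15% to 46% and power for +1.3 mm² is 42% to 85%, depending on the SDs and on the form of the t-test.

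The reach is limited to secondary objective 2.2.1. The primary tibial test is untouched. The within-patient correlations (2.2.2 to 2.2.4) do not use the controls and are unaffected as long as every patient is scanned at the same level, which the blank Appendix H field does not ensure. The point should be fixed before the sural comparison is read.

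**What to change.** 1. From the primary control data the sponsor already holds, establish the landmark at which the 60 controls' sural nerves were scanned. If the data set does not record it, take it from the documentation of that study's scanning procedure.
2. Correct Section 1.0 or Section 4.6 so that both name that landmark.
3. State in Section 4.6, and pre-print in the probe-location field of Appendix H: 'The sural CSA compared with the historical controls is measured at [landmark in the control data] in every patient.'
4. If patients have already been scanned, read the site from Appendix H, use only site-matched scans in the control test, and report how many matched.

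The cost is one look-up, one wording change and one pre-printed line, with no extra patients or staff. Step 4 can cost some precision. With 22 matched scans the detectable difference at 80% power is 0.707 × 1.8 = 1.27 mm²; with 20 it is 0.732 × 1.8 = 1.32 mm². The detectable difference should therefore be restated for the number matched.

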4.7 Follow-up

Results of diagnostic testing will be made available in the participant's medical record. If unexpected abnormalities are detected, the primary oncologist will be contacted and a Neurology referral can be placed as part of the patient's routine clinical care. The patient will also be followed for 30 days to ensure the biopsy site is healing adequately. This follow up may be by telephone or in person.

4.8 Data entry/storage

Paperwork with identifying patient information will be stored at the investigator's workspace in the locked workroom of the Hem/Onc 1st floor Watlington office or in the lab notebook of [name] in his locked lab; both are located on the WFBMC campus. Electronic data will be stored on the secure personal computers of the investigators on the medical center campus prior to transfer into the secure RedCap online database.

5.0 Outcome Measures

Listed below are the primary, secondary and exploratory outcomes. However, given this is a pilot study, other parameters associated with nerve conduction and ultrasound studies will be captured and may be used for exploratory analyses and will include, but will not be limited to latency for nerve conduction studies and for ultrasound, echogenicity, vascularity, fascicle concentration, and other qualitative descriptions of nerve changes.

5.1 Primary Outcome

5.1.1 Tibial nerve CSA as determined by ultrasound in the tibial nerve in TIPN patients and derived from historical controls.

5.2 Secondary Outcomes

5.2.1 Sural nerve CSA as determined by ultrasound of the sural nerve in TIPN patients and derived from historical controls.

5.2.2 Amplitude, distal latency, and conduction velocity of nerve response derived from NCS in TIPN patients.

5.2.3 Self-reported neuropathy score as assessed by the EORTC QLQ-CIPN20.

5.2.4 Nerve fiber density in the skin (IENF/mm) in TIPN patients.

5.3 Exploratory Outcome

5.3.1 The number of activated mast cells (per mm) in TIPN patients

5.3.2 Serum levels of inflammatory molecules in TIPN patients chosen at the investigators discretion

5.4 Covariates

5.4.1 BMI

5.4.2 Age

5.4.3 Breast cancer staging

5.4.4 Types/dosages of chemotherapy and corticosteroids received

5.4.5 Presence of previously documented comorbidities (diabetes, B12 deficiency, thyroid disorders, alcoholism, depression, carpal tunnel syndrome, sciatica)

5.4.6 Use of analgesics or treatments for neuropathy

5.4.7 History of clinically documented compressive neuropathy (carpal tunnel syndrome)

6.0 Analytic Plan

6.1 Sample Size and Power

6.1.1 Primary outcome:

This current study will enroll a sample size of 22 in TIPN patients to compare to historical data that was previously collected from 60 healthy patients. Using a two-sided test and significance level of 0.05, we will have an 80% power to detect an effect size of 0.73 (unit: standard deviation [SD]) when comparing TIPN patients to that historical data. We have permission to utilize historical data (primary data) collected from healthy patients which found that the mean and SD of the tibial nerve CSA were 14.2 and 4.4 mm², respectively (published by Cartwright et al., 2008). Assuming the same SD in TIPN patients, we will have more than 80% power to detect a difference of 3.2 mm² for the tibial nerve. Based on Riazi et al. (2012),³² the mean increase in size of tibial nerve was 5.3 when comparing subjects with diabetic sensorimotor polyneuropathy and control subjects. Even though the study sample is not exactly the same, with the minimal detectable difference equal to 3.2, we should have sufficient power for this analysis.

6.1.2 Secondary outcome:

In historical data collected from healthy patients (Cartwright et al., 2008),⁸ the mean and standard deviation (SD) of the sural nerve CSA were 5.3 and 1.8 mm², respectively. Assuming the same SDs in TIPN patients, we will have more than

80% power to detect a detectable difference of 1.3 mm² for the sural nerve between TIPN patients and healthy patients.

6.2 Analysis of Primary Outcome

The distribution of the primary outcome, nerve CSA, will be transformed to satisfy conditional normality assumption if necessary. It will be compared to the historical data from healthy patients using two-sample t-test (two-sample t-test selected as primary data from the historical control patients is available and will be used for analysis). We will also compare the nerve CSA in our study sample to that in the historical diabetic neuropathy patients and historical oxaliplatin neuropathy patients using one-sample t-test. The general linear model will be used to evaluate any factors (e.g., age) that may be associated with the nerve CSA. Due to the limited sample size, no more than two covariates will be included in the model.

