To date, there has only been one small study assessing US detection of chemotherapy-induced peripheral neuropathy; this was done among colorectal cancer patients who had received oxaliplatin. Similar to several other etiologies of nerve lesions/neuropathies, this study also found an increased peripheral nerve CSA compared to reference values. Interestingly, although the patients had denied symptoms of neuropathies at time of recruitment, this study found areas of increased peripheral nerve CSA at upper extremity sites of entrapment such as the carpal tunnel and ulnar groove; it did not find US abnormalities in terms of CSA or echogenicity at the sural nerve or other sites.¹⁰ Oxaliplatin has a much different mechanism of action from the taxanes; as a platinum-based agent it causes DNA cross-linking which inhibits cancer cell growth. Oxaliplatin-induced neuropathy is also a distinct entity that is characterized by cold sensitivity and mediated by prolonged opening of sodium ion channels along neuronal axons.¹¹ On a review of publications in the MEDLINE database as well as abstracts from the American Society of Clinical Oncology, we did not find any other prior studies that focused on the use of US to detect chemotherapy-induced peripheral neuropathy, and none for TIPN.

As noted above, there are currently several different diagnostic modalities that can assess TIPN, including self-reported symptoms, physical examination, nerve conduction study, sudometer testing, and skin biopsies. But each have limitations so that none have emerged as a widely-adopted standardized approach.

In routine practice, most clinicians rely on patients' self-reported symptoms alone for TIPN detection. These symptoms can be measured on one of several clinician-administered grading scales, although these have inter-scale and inter-observer variability.¹² The European Organization for Research and Treatment of Cancer (EORTC) QLQ-CIPN20 Questionnaire is a 20-item self-reported survey that is easy to administer and was validated across participants in four large cooperative group trials.¹³ Furthermore, although in many patients the development of acute TIPN symptoms is predictive of eventual chronic TIPN,¹⁴ some patients develop a disproportionately delayed TIPN that is not able to be self-reported early enough to allow for intervention.

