6.3 Analysis of Secondary Outcome

The analysis of sural sensory nerve CSA will be the same as that specified for primary outcome. To examine the associations between nerve CSA and NCS measures, the self-reported neuropathy scale, and intraepidermal nerve fiber density, Spearman's rank correlation coefficient will be used. The general linear model will be also used to evaluate the association after adjusting for one or two risk factors (e.g., age). Nerve CSA will be treated as the dependent variable. NCS measures, the self-reported neuropathy scale, and intraepidermal nerve fiber density are the covariates of interest. They will be fitted in the model one at a time.

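### The sural nerve is to be tested against healthy and diabetic references whose healthy baselines are 5.3 and 1.40 mm², so the two comparisons cannot both be valid

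*Combined protocol and SAP*

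**What the plan says.** Section 6.2 is written for the primary (tibial) outcome. It plans a two-sample t-test against primary data from the healthy historical patients, and then adds: "We will also compare the nerve CSA in our study sample to that in the historical diabetic neuropathy patients and historical oxaliplatin neuropathy patients". The method for these added comparisons is a one-sample t-test. Section 6.3 brings in the sural nerve: "The analysis of sural sensory nerve CSA will be the same as that specified for primary outcome". The sural nerve is therefore tested against both the healthy and the diabetic reference. The only adjustment mentioned is a transformation for normality. Nothing is said about measurement site or source, and the diabetic series is not named.

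The values are in Section 1.0. The healthy reference is introduced as "Ultrasound measurements of the sensory sural nerve at the distal calf in healthy participants", who "had an average CSA of 5.3 mm² with standard deviation 1.8 mm²"; Section 6.1.2 uses the same mean and SD for planning. Section 1.0 then describes a study done further down, at the ankle. It reports smaller areas, with enlargement in diabetic "polyneuropathy as compared to healthy controls (mean/standard deviation 2.59 / 0.96 mm² as compared to 1.40 / 0.59 mm²".

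Section 4.6 says this trial measures the sural nerve at the ankle, yet it bases technique and reference values on the institutional data that Section 1.0 places at the distal calf.

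**The concern.** A one-sample test against a published mean makes sense only if that mean is on the same measurement scale as the new data. Healthy people are the natural check on scale, and here the two sources disagree: 5.3 against 1.40 mm². The gap of 3.9 mm² is three times the 1.3 mm² that the sural comparison is sized to detect. The diabetic mean of 2.59 mm² even lies inside the normal range of 1.7 to 8.9 mm² that Section 1.0 gives for the healthy reference.

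Whichever scale the study's sonographer works on, one of the two planned sural tests would show a large, highly significant difference that reflects landmark or laboratory and not taxane exposure. The analysis section does not say how this would be recognised or handled.

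**Working it through.** **Inputs.** TIPN n = 22, healthy n = 60, two-sided alpha 0.05 (Section 6.1.1). Healthy sural mean 5.3, SD 1.8, same SD assumed in TIPN, detectable difference 1.3 mm² (Section 6.1.2). Diabetic 2.59 (SD 0.96) and that study's controls 1.40 (SD 0.59) (Section 1.0).

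**1. The plan's own figure.** Effect size 1.3/1.8 = 0.722. Noncentrality 0.722 × √(22×60/82) = 2.90 on 80 df. Power is 81.7%, which agrees with the stated figure of more than 80%.

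**2. Are the healthy baselines different beyond chance?** Ratio 5.3/1.40 = 3.8; difference 3.9 mm². The size of the second control group is not given. Even if it were only 10 (my assumption), the standard error is √(1.8²/60 + 0.59²/10) = 0.298, so the gap is about 13 standard errors.

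**3. Branch A: study nerves read on the 5.3 scale.** Suppose TIPN nerves are exactly normal (mean 5.3, SD 1.8, n = 22).
- t = (5.3 − 2.59)/(1.8/√22) = 2.71/0.384 = 7.06 on 21 df, p about 6e-7. The difference is +2.71 mm² (95% CI 1.91 to 3.51).
- The probability of rejection is above 99.99%. It stays at or above 98% for any assumed SD from 0.59 to 3.0.
- Adding sampling error in the diabetic mean, with 10, 50 or 100 diabetic patients assumed, gives ratios of 5.5, 6.7 and 6.9.
- Any sample mean above 2.59 + 2.08 × 0.384 = 3.39 mm² tests as larger than diabetic.

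Against its own controls the diabetic group is (2.59 − 1.40)/0.59 = +2.0 SD, a ratio of 1.85. The table carries that shift to the 5.3 scale and repeats the test on a normal sample.

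| Conversion | Diabetic value (mm²) | t for a normal sample |
|---|---|---|
| Ratio | 5.3 × 1.85 = 9.8 | −11.7 |
| Control SDs | 5.3 + 2.02 × 1.8 = 8.9 | −9.5 |
| Absolute difference | 5.3 + 1.19 = 6.5 | −3.1 (p = 0.005) |

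The sign reverses under all three conversions.

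**4. Branch B: study nerves read near 1.40.** The diabetic comparison is now on scale, and the healthy one fails.
- Normal nerves (1.40, SD 0.59): pooled SD √[(21×0.59² + 59×1.8²)/80] = 1.575, and t = −3.9/(1.575 × √(1/22 + 1/60)) = −9.9.
- Nerves as enlarged as the diabetic ones (2.59, SD 0.96): pooled SD 1.622, and t = −2.71/(1.622 × 0.249) = −6.7. Enlarged nerves would be reported as smaller than healthy.

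**5. Why standardising alone is not enough.** In Branch B, scoring against the 60 controls puts normal nerves at (1.40 − 5.3)/1.8 = −2.2 SD and diabetic-sized nerves at (2.59 − 5.3)/1.8 = −1.5 SD. The landmark has to be settled before any standardisation.

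**The case against.** The strongest objection concerns direction. A reader might infer from Branch A that the plan is bound to report TIPN nerves as larger than diabetic ones. The documents do not support that. Section 4.6 puts the trial's sural measurement at the ankle, which is the diabetic study's site, so the diabetic comparison may be the like-for-like one and the healthy comparison the faulty one. Section 4.6 also ties the reference values to the 5.3 mm² source, so the question is open. This objection stands, and the point is therefore stated as two branches.

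Three limits on scope also stand:
- Section 6.2 does not name its diabetic series. The value 2.59 is used because it is the only diabetic sural mean given.
- A reader might extend the mismatch to the tibial nerve. Section 6.1.1 gives only a diabetic increase of 5.3 and no diabetic tibial mean, so no tibial mismatch can be shown.
- A reader might extend it to oxaliplatin. Section 1.0 gives no oxaliplatin CSA value and mentions reference values, not a control group, so no scale error can be shown. It does report enlargement at upper-extremity entrapment sites. What remains is that "although the patients had denied symptoms of neuropathies at time of recruitment" and that the study found no sural abnormality, whereas this trial enrols patients with documented symptoms.

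Finally, no listed objective or outcome calls for the diabetic comparison. It is ancillary, on a secondary nerve, in a 22-patient pilot. That limits the importance of the diabetic test, but in Branch B the test that fails is the sural-versus-healthy comparison, which is a stated secondary objective.

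**Conclusion.** The concern holds for the sural nerve, in conditional form: on the protocol's own figures, the healthy and diabetic sural comparisons cannot both be valid. The test that is off scale would give t of about 7 (normal nerves declared larger than diabetic) or about −10 (normal nerves declared smaller than healthy).

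This rests on 2.59 mm² being the diabetic comparator, on the stated SDs, and on study nerves reading near one of the two healthy baselines. If they read in between, neither comparison is on scale. A normality transformation does not help: it leaves the scale difference in place, and transformed data could not be tested against an untransformed published mean. The documents do not show which branch applies. The primary tibial-versus-healthy test is unaffected. The change is worth making before analysis but does not threaten the study's main result.

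**What to change.** 1. Reconcile Sections 1.0, 4.6 and 6.1.2 on the sural scanning landmark. Use the healthy-control sural data only if they were taken at that landmark; Section 6.2 says the primary data are available, so this can be checked.
2. In Section 6.3, replace the raw sural-versus-diabetic t-test with TIPN versus landmark-matched healthy controls, as a standardised difference or a ratio with confidence interval. Set it beside the published diabetic-versus-own-controls difference. Name the diabetic source and choose one metric in advance, because relative spread differs between sources (0.59/1.40 = 42%; 1.8/5.3 = 34%).
3. Keep a raw test only where nerve, landmark and healthy baseline agree between sources. Apply the same condition to any tibial comparison, noting that the documents show no tibial mismatch.
4. Make any oxaliplatin comparison descriptive, stating that the cited patients had denied symptoms at recruitment and had no sural CSA abnormality.

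The cost is a few sentences and a check of the control records. An ancillary comparison becomes descriptive instead of yielding a p-value. A confidence interval for the diabetic difference needs that study's group sizes, which the protocol does not give. If the control data turn out to be from another landmark, the sural-versus-healthy comparison has no matched control group, and that is better known before analysis than after.

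### The planned t-test against historical oxaliplatin patients mixes drug with symptom status, so it cannot support a taxane-versus-oxaliplatin neuropathy conclusion

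*Combined protocol and SAP*

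**What the plan says.** The primary outcome is "Tibial nerve CSA as determined by ultrasound in the tibial nerve in TIPN patients and derived from historical controls" (Section 5.1). Its main analysis is a two-sample t-test against 60 healthy historical controls. Section 6.2 then adds a supplementary analysis, to "compare the nerve CSA in our study sample to that in the historical diabetic neuropathy patients and historical oxaliplatin neuropathy patients using one-sample t-test". Section 6.3 extends it: "The analysis of sural sensory nerve CSA will be the same as that specified for primary outcome".

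Section 6.2 gives no source, nerve site or null value for the oxaliplatin comparison, and does not say how a result would be interpreted. No objective in Section 2 asks for it.

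The background (Section 1.0) points to one candidate source, saying that "there has only been one small study assessing US detection of chemotherapy-induced peripheral neuropathy", in colorectal cancer patients who had received oxaliplatin. Three statements about that study matter here:

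- Symptoms: "although the patients had denied symptoms of neuropathies at time of recruitment".
- Where nerves were enlarged: the study "found areas of increased peripheral nerve CSA at upper extremity sites of entrapment such as the carpal tunnel and ulnar groove".
- Everywhere else: "it did not find US abnormalities in terms of CSA or echogenicity at the sural nerve or other sites".

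Section 3.1 of this trial requires neuropathy symptoms in the medical record that are suspected to come from the taxane. The study calendar (Section 4.2) limits ultrasound to the sural and tibial nerves, and Section 4.6 states: "Peripheral nerves will be assessed at non-compressive sites".

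**The concern.** A test labelled as one neuropathy against another invites a conclusion about the two drugs. The two groups, however, were selected on opposite criteria: patients here must have symptoms on record, while the oxaliplatin patients reported none at recruitment. The oxaliplatin study found enlargement where this trial does not scan, and nothing abnormal at the sural nerve, the one shared nerve that Section 1.0 names.

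A significant excess in the taxane group could therefore reflect drug, symptom status, or differences in site and technique between studies, and the test cannot tell these apart. Two things are at stake: an unsupported statement that taxane neuropathy enlarges nerves more than oxaliplatin neuropathy, and a second p-value that looks like independent support for the primary result when it may largely follow it.

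**Working it through.** **1. The two groups side by side**

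| | This trial | Oxaliplatin study, as described in Section 1.0 |
|---|---|---|
| Entry | Documented symptoms (3.1) | Symptoms denied at recruitment |
| Nerves and sites | Tibial and sural, non-compressive (4.2, 4.6) | Enlargement at arm entrapment sites; no abnormality at the sural nerve or other sites |
| Tibial CSA | Primary outcome | Nerve not named; no value |
| Sural CSA | Secondary outcome | No abnormality; no value |

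Drug and recruitment symptom status differ together, and there is no overlap from which to separate them.

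**2. Inputs for the size** (Section 6.1)

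22 TIPN patients, 60 healthy controls, two-sided 0.05. Tibial SD 4.4 mm², design difference 3.2 mm². Sural SD 1.8 mm², design difference 1.3 mm². Stated detectable effect 0.73 SD at 80% power.

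**3. The plan's own figure**

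Two-sample t-test, 80 df, non-centrality = d / √(1/22 + 1/60) = d / 0.2492.

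- d = 0.73: 0.73 / 0.2492 = 2.93, power 82.5%.
- Tibial d = 3.2/4.4 = 0.727: power 82.2%.
- Sural d = 1.3/1.8 = 0.722: power 81.7%.

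The plan's claim of at least 80% power holds, slightly on the conservative side.

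**4. The oxaliplatin test if that cohort's leg mean equals the healthy mean**

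This is an assumption, because the documents give no oxaliplatin leg mean, SD or sample size. One-sample t-test against a fixed value, n = 22, 21 df, non-centrality = difference / (SD/√22).

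- Tibial: 3.2 / (4.4/√22) = 3.41, significant in 90% of trials.
- Sural: 1.3 / (1.8/√22) = 3.39, significant in 90% of trials.

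These rates need no drug-specific effect; a shift from healthy values in symptomatic patients is enough.

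**5. Range over the assumed oxaliplatin mean**

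The TIPN shift is held at 0.73 SD above healthy. The difference tested is 0.73 minus the oxaliplatin shift.

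| Oxaliplatin mean relative to healthy (SD) | Difference tested (SD) | Significant |
|---|---|---|
| −0.25 | 0.98 | 99% |
| 0 | 0.73 | 90% |
| +0.25 | 0.48 | 57% |
| +0.5 | 0.23 | 18% |
| +0.73 | 0 | 5% |

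**6. Overlap with the healthy-control test**

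Both tests use the same 22 patients. Under the assumption in step 4, 100,000 simulated trials give:

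| True TIPN shift | Correlation of the two statistics | Same verdict |
|---|---|---|
| 0 | 0.85 | 95% |
| 0.73 SD | 0.77 | 88% |

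**7. Site and technique**

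Section 1.0 quotes healthy sural means of 5.3 mm² at the distal calf and 1.40 mm² at the ankle, from different studies. The gap is 5.3 − 1.40 = 3.9 mm², three times the 1.3 mm² design difference (3.9/1.3 = 3.0). A null value taken from another study at another site could decide the test in either direction.

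**The case against.** A reader might infer more: that the oxaliplatin cohort had normal leg nerves and no neuropathy, so that its label is misleading and the test is simply a second comparison with healthy nerves. The documents do not support that, for four reasons, all of which stand.

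- Symptoms were denied at recruitment. Symptom status at the scan is not given, and a patient without symptoms may still have neuropathy. Section 1.0 itself speaks of subclinical TIPN and presents the oxaliplatin work as a study of chemotherapy-induced neuropathy.
- Finding no abnormality in one small study does not show that the mean equals the healthy mean. The tibial nerve is covered at most by the mention of other sites.
- The 90% figure is one point on an unquantified range and falls to 5% within it. Even at that point the two tests disagree in 12% of simulated trials at the design effect.
- The comparator would be another study's mean, not the 60 institutional controls, so the test is not literally a repeat.

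It is also fair to say that Section 6.2 does not name the cohort. The link rests on Section 1.0 reporting that no other such study was found. The comparison is supplementary in a pilot, drives no decision, and the cohort's features are openly described in the background.

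These points limit the claim but do not rescue the test. Disclosure in Section 1.0 does not alter the analysis planned in Section 6.2. Adding a source and a null value would make the test reproducible, but drug and symptom status would remain confounded. Uncertainty about the oxaliplatin leg mean makes the result harder to interpret, not easier.

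**Conclusion.** The concern holds in a limited form. On the protocol's own description, the oxaliplatin comparison confounds drug with symptom status at recruitment, and possibly with measurement site and technique. Neither a significant nor a non-significant result would say how taxane neuropathy compares with oxaliplatin neuropathy.

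How often it would be significant cannot be fixed from the documents. At the design difference it is about 90% if the oxaliplatin leg mean equals the healthy mean, and 57%, 18% or 5% if that mean is 0.25, 0.5 or 0.73 SD higher. At the first of these values the test largely tracks the healthy-control test. These figures assume a common SD and treat the historical mean as fixed, as the planned one-sample test does. The confounding itself does not depend on them.

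The severity is minor: the primary healthy-control comparison and its power are untouched.

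**What to change.** Remove the oxaliplatin t-test from Section 6.2, which also removes it from Section 6.3. The comparison with diabetic neuropathy patients in the same sentence is not part of this point.

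If the sponsor wants to keep a reference to oxaliplatin, show the published CSA for the same nerve and the same site descriptively, with its source and no p-value. Label it: *oxaliplatin-treated, no symptoms reported at recruitment; no CSA abnormality reported outside upper-limb entrapment sites; not a comparison of neuropathies*. Where no value exists for that nerve and site, show none.

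The cost is an edit to one sentence and the loss of one supplementary p-value per nerve. No objective, sample size or data collection changes.
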